NCT03506438

Full Title: Addressing Palliative Care Needs Among Intensive Care Unit Family Members

Document Date: 04/28/2021

Protocol (Pro00090202)

Research Abstract

Please type your Research Abstract here:

The Research Abstract should summarize the main points of your study in one paragraph. The following quidelines may help you:

- 1. Purpose and objective (1-2 sentences)
- 2. Study activities and population group (2-4 sentences)
- 3. Data analysis and risk/safety issues (1-2 sentences)

This 5-year project funded and conducted under Duke's REACH Equity Center, run by PI [name]. The blanket protocol number for the REACH Equity Center is Pro00090554.

The purpose of the study is to test and develop a web application (ICUconnect) that will improve racial disparities and unmet palliative care needs among ICU family members using a randomized clustered clinical trial (RCT). An ancillary study will be conducted simultaneously to determine if the presence of 'palliative care triggers' among patients is associated with greater unmet needs among patients' family members.

We anticipate that our total study population across both the RCT and ancillary studies will include, in total, 360 patients, 395 family members, and 60 physicians. The clinical trial group will consist of 160 family members of patients (80 white and 80 black) in Duke ICUs (medical, surgical, cardiac, cardiothoracic and neurological, including DRH ICU). A total of 200 family members will participate in the ancillary study, 130 of whom will be enrolled as the control group in the clinical trial (including up to 30 who otherwise would have been deemed ineligible after T1 based on a low needs score i.e., NEST survey) and 70 others. 10 family members will complete app user testing alone and will not be trial participants (Aim 1 Usability) and up to 25 family members previously enrolled in aim 2 of the RCT and ancillary studies will be asked to participate in Aim 4 of the RCT (or Aim 3 of the ancillary study).

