
Aims 2 and 3 of the RCT will be completed simultaneously. The total targeted population for Aims 2 and 3 of the RCT are 240 enrolled patient/family dyads and a maximum of 60 randomized clinicians. To be considered "enrolled" for this study, a patient/family dyad must meet all eligibility criteria and receive a NEST score of > 15.

For aims 2 and 3, the study team will conduct a randomized clustered clinical trial. Randomization occurs at the ICU clinician level versus that of the patient/family level. Clinicians are identified as eligible if they are the current attending on service for the particular ICU. Clinicians are randomized to one of the two arms based on the following:

- 1. Gender (male/female)
- 2. Clinical Experience (<10 years vs > 10 years)
- 3. Discipline (medical vs. surgical)

Consented, enrolled clinicians are expected to complete the following survey(s):

• Baseline Demographics Survey (on the day of consent)

For those clinicians who are randomized to intervention, they will be required to complete the following:

- Review patient/family needs score and survey results within ICUconnect (at the completion of T1 by patient/family dyad)
- Schedule and conduct a family meeting (after T1 completion but before T2 completion)
- Review patient/family needs score and survey results within ICUconnect (at the completion of T2 by patient/family dyad)
- Complete the Clinician Survey via ICUconnect (after Family Meeting and completion of T1 and T2 by patient/family dyad).

Patient/family dyads will be identified at the time of ICU admission and approached for consent based on meeting study inclusion/exclusion criteria (see Selection of Subjects). Each patient/family member, if enrolled into the RCT will be asked to complete an ICUconnect profile and survey (T1). This survey is to be completed within 24 hours of consent to the study. Given that this study's intent is to address unmet needs, eligible participants must receive a NEST score of > 15 (see Study Eligibility Workflow).

- If a participant receives a NEST score of < 15 and they are assigned to a randomized intervention clinician, the participant is considered a screen failure.
- If a participant receives a NEST score of < 15 and is assigned to a randomized control clinician, the
 participant is considered a screen failure for the RCT but is allowed to continue participation within
 the ancillary study.

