General considerations: The primary analyses will be conducted on an intention-to-treat basis; clinicians and patients will be analyzed in the group to which they were randomized, regardless of clinician intervention adherence, using all available data. The main conclusions drawn from this trial will be based on the pre-specified hypotheses outlined below and will be tested with two-sided p-values at the standard 0.05 level. For all study outcomes, we will interpret differences between groups over time with reference to prior literature regarding clinically meaningful changes. Results from exploratory analyses will be interpreted with appropriate consideration for their exploratory nature. Statistical analyses will be performed using the latest release SAS for Windows (Cary, NC) and R/Rstudio.

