Approach to statistical models: The goal of the primary hypothesis (2a) is to determine the efficacy of the ICUconnect intervention versus usual care on reduction in unmet needs from T1 to T2. Additionally, we are interested the intervention effect within Black families and White families separately. Unmet needs will be assessed at T1 and T2 with the total NEST score, a continuous, normally distributed measure. Because each family member is surveyed at multiple time points and the same ICU physician sees several patients, outcome variable measurements will not be independent. We, therefore, plan to use hierarchical linear models as our primary analytic strategy because they appropriately account for the multiple types of correlation inherent in our study design.45 The hierarchical linear model will have the following form: Yijk= b0+ b1(T2) + b2(T2*intk) + b3(racek)+ b4(servicetimek) + b5(ICUtypek)+ bik+ ck+ eijk, where Yijkis the total NEST score for family iat time jand physiciank. In this model, T2and intare indicator variables for the post-treatment and intervention group, respectively. Additionally, we include indicators for the randomization stratification variables. The multiple levels of correlation are captured via the physician-level random effect, ck, and the family-level random effect, bjk. Both random effects and the residual error (eijk) are assumed to be independent and normally distributed. PROC MIXED in SAS (SAS Inc., Cary, NC) will be used to fit the hierarchical linear models and test the primary hypothesis (2a). Specifically, if b2is negative and significantly different than zero, this provides evidence families in the intervention group have reduced unmet needs as compared to usual care group families. The secondary outcome, quality of patient-centered care, is also a continuous measure assessed at T1 and T2. A similar hierarchical linear model will be used to test Hypothesis 2b; in this model, if b2is positive and significantly different than zero, this provides evidence families in the intervention group have improved quality of patient-centered care as compared to usual care group families. Both analyses for Hypotheses 2a and 2b will be repeated within Black and White patients separately, with the goal to ensure that the intervention is effective in both subgroups (as an overall treatment effect can sometimes mask important heterogeneity). Aim 3 addresses relative differences in the intervention effect on reducing disparities.

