Aim 3 Analyses: A hierarchical linear model will again be the primary modeling strategy for the Aim 3 analyses. For this Aim, however, the model will include patient-race interaction terms and will have the following form: Yijk= b0+ b1(Blacki) + b2(T2) + b3(T2*Blacki) + b4(T2*intk) + b5(T2*Blacki*intk) + b6 (racek)+ b7(servicetimek) + b8(ICUtypek)+ bik+ ck+ eijk, where Yijkis the NEST score for family iat time jand physician k. In this model, Blackiis the indicator variable for whether a patient is Black (value of 1) or White (value of 0). Racial disparities in unmet needs at baseline are represented by the estimated value of b1. That is, the estimated baseline mean for White families is b0 and the estimated baseline mean for Black families is b0 + b1, so if the estimate of b1is positive, this indicates that prior to the intervention, Black patients have more unmet needs than White patients. Post-treatment, the Black-white mean difference among usual care group families is BWuc = (b0 + b1 + b2 + b3) - (b0 + b2), and among intervention group families is BWint = (b0 + b1 + b2 + b3 + b4 + b5) - (b0 + b2 + b4). Hypothesis 3a will be tested by the difference between BWint and BWuc, indicating that racial disparities unmet needs are reduced in the intervention group as compared to the control group. The estimated difference, p-value, and 95% confidence intervals will be calculated via estimate statements in PROC MIXED. Additionally, estimated values and confidence intervals will be calculated for BWint as compared to b1 to quantify the magnitude of reduction from baseline. A similar hierarchical linear model will be used to examine the reduction in racial disparities of quality of patient-centered care and test Hypothesis 3b.

Missing Data: The survey data may contain missing values in any of the clinician-level and patient-level variables due to drop-out, death, or item non-response. Our primary analysis technique, hierarchical models, allow for unbalanced or incomplete data and will be fit with maximum-likelihood methods to preserve the missing at random assumption. Additionally, we will thoroughly explore reasons for dropout, and depending upon the type and scope of missing data, variables may be multiply imputed as recommended by guidelines.46Note that if needed, we will utilize imputation methods that account for the multiple levels of correlation inherent in the clustered data structure.

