
Power and sample size considerations. For Aim 1, to reach a target of 'excellent' usability (mean SUS score >85), we expect 1-2 iterative revision cycles of 8-15 family members and 8-10 clinicians—a sample similar in size to that needed to reach thematic saturation in qualitative analysis (e.g., the 30 patient-level cases (total n=90) we expect will allow us to recognize theme saturation in Aim 4). The effect of interest for Aims 2 and 3 is essentially the T1 - T2 difference between the intervention and usual care groups. Aim 2 focuses on the overall difference and the difference within Black and White patients separately, while Aim 3 focuses on the difference within Black families compared to White families. Therefore, we base our sample size calculations on the mean difference score using tests for two means in a cluster randomized design. The sample size requirements are greatest for Aim 3; as discussed by Leon and Heo (2009), the needed sample size for the family race by intervention group interaction is 4 times that needed for the overall test. Based on preliminary studies, the standard deviation of the change in NEST score is estimated as 12 units and a reasonable range of intraclass correlation coefficients is 0.01 to 0.1. For all calculations, the type I error is 5% and power is 80%. With a sample size of 160 families (4 per each of 40 physicians. 20 per treatment arm), we will be able to detect differences of 4.0 to 5.0 NEST units for Hypothesis 2a in the overall test, 5.4 to 6.1 for Black or White patients separately, and 7.6 to 8.0 units for Hypothesis 3a. For Aim 4, we expect that up to 25 cases comprised of family members will be sufficient to reach informational redundancy—the point at which no new themes emerge.

Ancillary study: Needs and triggers: improving intensive care unit-based palliative care deliveryStatistical methods:

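### The Aim 2 primary model omits family race, giving up some precision and any protection of b2 against a chance racial imbalance between arms; its covariates also do not match the listed strata

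*Protocol*

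**What the plan says.** Under Approach to statistical models (Aim 2 Analyses), the Protocol gives the primary model as "Yijk= b0+ b1(T2) + b2(T2*intk) + b3(racek)+ b4(servicetimek) + b5(ICUtypek)+ bik+ ck+ eijk". The three covariates carry the physician subscript k and enter as main effects only. The text describes them as the variables used to stratify randomisation.

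The Aim 3 model in the next section contains "b1(Blacki) + b2(T2) + b3(T2*Blacki) + b4(T2*intk) + b5(T2*Blacki*intk") and then the same three physician covariates. Family race therefore appears there as a level term, in interaction with T2, and in the three-way term with treatment.

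The Research Abstract plans "160 family members of patients (80 white and 80 black"), an overall target with no split by arm. Design & Procedures states that "Randomization occurs at the ICU clinician level versus that of the patient/family level" and lists the clinician's gender, clinical experience and discipline as the factors for randomisation.

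The SAP names hierarchical linear models for the primary outcome but gives no equation and no covariates.

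**The concern.** race_k in the Aim 2 equation cannot be family race, because the Aim 3 equation carries it alongside Black_i. The primary model thus fixes at zero two effects, race on level and race on change, that Aim 3 estimates on the same families and the same outcome.

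The coefficient b2 decides Hypothesis 2a. Two things are at stake. If the arms happen to differ in racial mix, part of any race difference in level or change is carried into this trial's estimate of b2. Race-related variation also stays in the error term. The trial already holds the data needed to remove both.

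Separately, the covariates said to be the strata are not the listed ones. Gender is a stratum but is not in the model. Physician race is in the model but is not a listed stratum. Service time and ICU type presumably stand for experience and discipline, though the text does not say so.

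**Working it through.** **Inputs from the Protocol.** From Power and sample size considerations: "the standard deviation of the change in NEST score is estimated as 12 units"; "a reasonable range of intraclass correlation coefficients is 0.01 to 0.1"; "the type I error is 5% and power is 80"%; 160 families, 4 for each of 40 physicians. Tests are two-sided at 0.05 (General considerations). Design & Procedures and Subject Recruitment give a target of 240 families and up to 60 clinicians.

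**Assumptions.** The documents give none of these:
- rho, the T1-T2 correlation within a family: 0.3, 0.5, 0.7.
- L, the Black-White gap in NEST level (b1 in the Aim 3 model), and C, the gap in T1-T2 change (b3 in the Aim 3 model).
- d, the difference between arms in the share of Black families.
- A change SD of 12 gives a residual variance of 144/2 = 72. Physician clustering of the outcome is left out of the shift and variance formulas.

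**Yardstick.** The Protocol states a detectable difference of 4.0-5.0 for Hypothesis 2a. The standard cluster formula, (1.960 + 0.842) × 12 × √(2 × DE/80) with DE = 1 + 3 × ICC, gives 5.39 at ICC 0.01 and 6.06 at ICC 0.1. The stated range does not reproduce at 160 families. That is a separate matter, so both ranges are used for comparison.

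**Size of d.** With 80 families per arm and half of them Black, SD(d) = √(0.25 × 2/80) = 7.9 points. With a design effect of 1.3 for racial clustering by clinician it is 9.0 points. An imbalance beyond 15 points then has probability of about 6-10%. With 120 per arm (240 families, 4 per clinician) the SD is 6.5-7.4 points and that probability is about 2-4%.

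**Shift in b2.** The model has no treatment main effect, so baseline means are taken as equal. The treatment contrast then weighs T2 against rho times T1. A race effect of L at T1 and L + C at T2 enters as

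shift = d × [C + (1 − rho) × L].

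**Variance.** Per family, the variance of T2 − rho × T1 is 72 × (1 + rho). Omitting race adds [C + (1 − rho)L]²/4, multiplied by 1.3 if race clusters by clinician. The reduction from adjustment is the added part over the total. For L = C = 5 and rho = 0.3: 8.5²/4 = 18.1 against 72 × 1.3 = 93.6, so 18.1/111.7 = 16%. With clustering, 23.5/117.1 = 20%.

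| Level gap L | Change gap C | Shift at d = 15 points, rho 0.3 to 0.7 | Variance reduction |
|---|---|---|---|
| 5 | 5 | 1.28 to 0.98 | 8-20% |
| 3 | 3 | 0.77 to 0.59 | 3-8% |
| 5 | 0 | 0.53 to 0.23 | 0-4% |
| 5 | −2.5 | 0.15 to −0.15 (0 at rho 0.5) | about 0% |
| 5 | −5 | −0.23 to −0.53 | 1-3% |
| 0 | 0 | 0 | 0% |

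At a one-SD imbalance with 160 families, gaps of 5 give 0.079 × 6.5 = 0.5 to 0.090 × 8.5 = 0.8 units.

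**Which terms are needed.** A race main effect alone removes the level part but leaves about (1 + rho)/2 of the change part. With C = 5 and d = 15 points that is 0.15 × 5 × 0.65 = 0.49 to 0.15 × 5 × 0.85 = 0.64 units. With Black_i and T2*Black_i together the shift is zero.

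**T2-by-stratum terms.** Suppose the strata explain half of the between-physician variance in change. The variance factor goes from 1 + 3 × ICC to (1 − ICC) + 2 × ICC. That is 1.03 to 1.01 at ICC 0.01 (detectable difference 5.39 to 5.34) and 1.30 to 1.10 at ICC 0.1 (6.06 to 5.58).

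**The case against.** The strongest reply is that this is not bias. A reader might infer from the shift formula that b2 is biased or that the primary test is invalid. The documents do not support that: clinicians are randomised, so d has expectation zero. Simulation of the written model (160 families, without physician clustering of the outcome) gave a mean error in b2 of about zero. Type I error was 5.0-5.8% with gaps of 3 or a level gap of 5 only, and 5.7-6.5% with both gaps at 5, against 5.0-5.8% with both race terms. This objection stands. One reservation remains: families are consented under an already randomised clinician, and some leave after T1, so imbalance could be systematic. Nothing in the documents shows that it is.

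A reader might also take 1.0-1.3 units as the typical error. It needs a 15-point imbalance and gaps of 5 in the same direction, which means that the racial gap doubles from 5 to 10 between T1 and T2. If the group with greater need improves more, the two parts offset each other. This stands too.

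Third, race is partly covered. Hypotheses 2a and 2b are repeated within Black and White patients, where racial mix cannot matter, and a race-adjusted overall effect could be derived from the Aim 3 model. But neither is the declared primary test, and the overall b2 stays unadjusted.

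Finally, clinicians are stratified at randomisation, so the strata can become unbalanced only through the number of families per clinician. That makes T2-by-stratum terms a minor matter.

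**Conclusion.** The omission is real on the page, and the SAP does not repair it. Its cost is lost precision and lost protection against imbalance in a single trial; it is not expected bias. With rho of 0.3-0.7, a 15-point imbalance moves b2 by 0 to 1.3 NEST units, against a detectable difference stated as 4.0-5.0 and recomputed as 5.4-6.1. The upper end requires two gaps of 5 with the same sign. The variance saving runs from nothing to about 20% under the same assumptions. At 240 families large imbalances are rarer. Since the size and sign of the gaps are unknown, the case for change rests on its being nearly free and consistent with the Aim 3 model. The mismatch between the listed strata and the model's covariates is a plain contradiction and needs resolving in any case.

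**What to change.** 1. Under Approach to statistical models, add Black_i and T2*Black_i to the Aim 2 model for Hypotheses 2a and 2b. Keep b2 as the single primary coefficient.
2. Write the same equation, with its covariates, into the SAP.
3. Reconcile the list of strata in Design & Procedures with the covariates in the Aim 2 and Aim 3 equations, and enter the strata actually used for randomisation in both models. If physician race stays, describe it as an additional covariate.
4. Treat T2-by-stratum terms as optional; they gain little unless the physician ICC is near 0.1.
5. The SAP is written in the past tense. If b2 has already been estimated, report the race-adjusted fit as a labelled sensitivity analysis.

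The cost is a few fixed-effect parameters and some wording. No new data are needed.

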Please note that for all scenarios described above, a research introduction may also be completed by the investigators of this study, as they all are routinely physicians on service and dually serve as members of the clinical care team. Research introductions for eligible patient/family dyads provided by investigators will be used as infrequently as possible and only when necessary. This will ensure that coercion to participate in the study is minimized as much as possible.

Eligible clinicians will be introduced to the research study by the investigators of the study. All eligible clinicians will be approached and provided a brief research introduction. If the clinician is interested in participation, he/she will provide verbal or written affirmation to the investigators. The investigators will then inform the study team of the clinician's interest in the study and confirm that it is okay to approach for research. The study team will then contact the clinician, due to their busy schedule, electronically and provide the eConsent (unless otherwise requested by the clinician, in which case paper consent would be utilized).

For the RCT, specifically, the study includes only those participants who self-identify as non-hispanic and either white or black. The purpose of this design is to determine racial disparities experienced among black patients and their families. However, the ancillary study is open to all races and ethnicities and will therefore ensure that the subject selection for this entire project is equitable and all relevant demographic groups have access to study participation.

To meet the statistical power needs for data analysis, the RCT intends to consent approximately 320 patient/family dyads to ensure that 240 patient/family dyads meet all study criteria and are subsequently enrolled. In order to enroll 240 patient/family dyads, 30-60 clinicians will be consented, enrolled and randomized to the study with a relatively equitable split between those clinicians assigned to intervention and those assigned to control.

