NCT03506438

Full Title: Addressing Palliative Care Needs Among Intensive Care Unit Family Members

Document Date: 04/28/2021

Statistical Analysis Plan (Pro00090202)

Statistical Analysis Plan

The goal of the primary hypothesis was to determine the efficacy of the ICUconnect intervention versus usual care on reduction in unmet needs from T1 to T2. Unmet needs were assessed at T1, T2, and T3 with the total NEST score, a continuous, normally distributed measure. Because each family member was surveyed at multiple time points and the same ICU physician saw several patients, outcome variable measurements were not be independent. Therefore hierarchical linear models fit via PROC MIXED in SAS 9.4 (Cary, NC) were used as the primary analytic strategy they appropriately accounted for the multiple types of correlation inherent in our study design. The other continuous, longitudinal outcomes included: PHQ-9, GAD-7, PTSS, and QOC; hierarchical linear models were also used to estimate the treatment effect over time for these outcomes. The binary outcomes of goal concordant care and IPC (dichotomized due to ceiling effects) were analyzed via generalized linear models with a logit link and fit with generalized estimating equations (PROC GENMOD in SAS, 9.4). Finally, treatment group differences in hospital and ICU length of stay were examined with a Wilcoxon test.

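### The Aim 2 primary model has no physician-by-time random effect, so the test of b2 omits physician clustering of change; type I error is about 5–10% in the powered design and up to about 15% with 30 clinicians

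*Protocol*

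**What the plan says.** The model is printed in the protocol under Aim 2 Analyses, Approach to statistical models. Its fixed part has an intercept, a T2 indicator, the T2-by-intervention product (coefficient b2) and three physician-level covariates. There is no intervention main effect, so the arms share one baseline mean. Its random part is a family intercept, a physician intercept and an independent residual: "The multiple levels of correlation are captured via the physician-level random effect, ck, and the family-level random effect, bjk". Hypothesis 2a is judged on b2. Hypothesis 2b uses a similar model, and "Both analyses for Hypotheses 2a and 2b will be repeated within Black and White patients separately". Under Missing Data, the models "will be fit with maximum-likelihood methods to preserve the missing at random assumption".

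Under Power and sample size considerations the protocol says "we base our sample size calculations on the mean difference score using tests for two means in a cluster randomized design". It takes an SD of change of 12 and states that "a reasonable range of intraclass correlation coefficients is 0.01 to 0.1". For 160 families (40 physicians with 4 each, 20 physicians per arm) it claims "we will be able to detect differences of 4.0 to 5.0 NEST units for Hypothesis 2a in the overall test". The recruitment section plans a larger trial: "In order to enroll 240 patient/family dyads, 30-60 clinicians will be consented, enrolled and randomized".

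The SAP says that hierarchical linear models were fitted in PROC MIXED. For the other longitudinal outcomes, "hierarchical linear models were also used to estimate the treatment effect over time for these outcomes". It gives neither a random-effects structure nor a degrees-of-freedom method.

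**The concern.** A physician intercept describes physicians whose families score higher or lower at both surveys. It cancels from the T2 minus T1 difference. The intervention acts between the two surveys, through the randomised physician's review of the results and the family meeting. If physicians differ in how much their families' scores change, that variation belongs in the error term for comparing arms of physicians. The printed model has no place for it and treats families of one physician as independent replicates of change.

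Because the baseline means are constrained equal, b2 is not a pure change-score contrast and draws on some between-physician information. Its standard error still leaves out the physician-by-time variance.

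The plan counts this clustering when it sizes the trial and drops it when it tests. A significant b2 could then partly reflect which physicians fell in which arm.

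**Working it through.** **Inputs from the protocol.** Two-sided test at 5%; SD of change 12; ICC 0.01 to 0.1; 40 physicians × 4 families; 240 dyads over 30 to 60 clinicians, that is 240/30 = 8 or 240/60 = 4 per physician. The ICC is read as that of the change score, the quantity to which the power section applies it.

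**The plan's own figure.** Detectable difference = (1.96 + 0.84) × 12 × √(2[1 + (m − 1)ICC]/n), with n = 80 families per arm and m = 4.
- ICC 0.01: 2.80 × 12 × √(2 × 1.03/80) = 5.4
- ICC 0.1: 2.80 × 12 × √(2 × 1.30/80) = 6.1

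The stated 4.0 to 5.0 is not reproduced. It matches 40 physicians × 8 families (t quantiles on 38 df: 3.99 to 5.03). That is a separate problem. What matters here is that the calculation inflates the variance of change by 1 + (m − 1)ICC, and the model does not.

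**Closed form.** If a change-score test ignores that factor, its type I error is 2[1 − Φ(1.96/√(1 + (m − 1)ICC))].
- 40 × 4, ICC 0.05: 1.96/√1.15 = 1.83, giving 6.8%
- 40 × 4, ICC 0.1: 1.96/√1.30 = 1.72, giving 8.6%
- 30 × 8, ICC 0.1: 1.96/√1.70 = 1.50, giving 13.3%

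**Simulation of the printed model.** The closed form ignores the baseline constraint, so null trials were generated and the model fitted as printed.
- *Set A* (REML, residual df; 2,000 to 3,000 trials per setting; Monte Carlo SE about 0.4 to 0.8 points). Variances: physician intercept 6, physician effect at T2 ICC × 144, family intercept 65; residual set so that the variance of change is 144. The T1–T2 correlation is about 0.5.
- *Set B* (maximum likelihood, Wald z, three physician-level covariates; 8,000 trials per setting). Baseline physician ICC 0.05. The physician effect on change was generated either equally at T1 and T2 or at T2 only.

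The splits of variance, the T1–T2 correlations and set B's baseline ICC are assumptions; the documents do not give them. Clusters are equal in size.

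| Design | ICC | Set A | Set B, equal at T1 and T2, to T2 only |
|---|---|---|---|
| 40 × 4 | 0.01 | 5.1% | 6.0–6.5% |
| 40 × 4 | 0.05 | 6.8% | 7.2–7.7% |
| 40 × 4 | 0.1 | 9.8% | 8.6–11.0% |
| 60 × 4 | 0.1 | 9.9% | 8.2–10.4% |
| 40 × 6 | 0.1 | 12.3% | 10.6–13.5% |
| 30 × 8 | 0.01 | 6.4% | 6.2–7.0% |
| 30 × 8 | 0.05 | 9.5% | 9.2–11.2% |
| 30 × 8 | 0.1 | 15.5% | 12.9–17.2% |

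With ICC 0 set A gives 5.2%, so the excess comes from the clustering. The mechanism shows in the standard error: at 40 × 4 and ICC 0.1 the model's mean SE is 1.68 against a true SD of b2 of 1.99. Then 2[1 − Φ(1.96 × 1.68/1.99)] = 2[1 − Φ(1.65)] = 9.8%.

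**Variants of set A at ICC 0.1, 40 × 4.**
- Three stratification covariates: 9.7%
- T1–T2 correlation 0.2 or 0.7: 10.8% and 10.4%
- Unequal clusters (CV of size about 0.65): 12.6%
- Physician effects equal at T1 and T2: 8.0% (30 × 8: 11.8%)

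The within-race repeat at ICC 0.1 gives 7.0% (40 × 2) and 10.4% (30 × 4).

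**With the missing term.** Set A with a physician-by-T2 effect and K − 2 df (K physicians) gives 3.9–5.4%. In set B, comparing physician-mean changes on K − 2 df gives 4.5–5.7%.

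**The case against.** The documents do not say how physician variance divides between T1 and T2. The higher figures assume that it arises at T2. If it is equal at both surveys, 40 × 4 at ICC 0.1 gives about 8–9% and 30 × 8 about 12–13%. At mid-range ICC in the powered design the excess can be as little as one point: one run with equal effects at ICC 0.05 gave 5.9%. The 15% figure also needs three things together: the top of the ICC range, the fewest clinicians, and all 240 dyads enrolled. The ICC range is a planning range and not evidence that change clusters at 0.1. The protocol does not say outright that it was estimated for change. Finally, the SAP mentions NEST at T1, T2 and T3, so percentages from a two-survey model do not carry over exactly to a three-survey fit.

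All of this stands as a condition on the size, and none of it supplies the missing term. Type I error exceeds 5% under both ways of generating the physician effect once the ICC is away from 0.01. Better degrees of freedom alone do not cure it: with the printed model and a t reference on K − 2 df, set B at ICC 0.1 still gives 7.5–10.0% (40 × 4) and 11.2–15.3% (30 × 8).

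**Conclusion.** The concern holds. As printed, the Aim 2 model omits physician clustering of change, and nothing in the SAP restores it. In the powered design, with equal clusters, true type I error at nominal 5% is about 5–6% at ICC 0.01, 6–8% at 0.05 and 8–11% at 0.1. With 240 dyads over 30 clinicians it is about 12–17% at ICC 0.1. Unequal clusters add to this. These sizes rest on reading the ICC as that of change and on assumed variance splits; the direction does not depend on the splits tried.

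The same structure carries over to hypothesis 2b and the within-race repeats. No inflation is claimed for the Aim 3 race-by-intervention contrast. Because this is the primary test, it should be corrected before the p-value for hypothesis 2a is relied on.

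A minor, related point: the SAP notes that one physician saw several patients and then compares length of stay with a plain Wilcoxon test. With an assumed ICC of 0.1 (the documents give none for this outcome), its type I error is 7.8–13.0% across designs from 40 × 4 to 30 × 8. At 0.01 it is 4.7–5.5%.

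**What to change.** In the Aim 2 models (2a, 2b and the within-race repeats), add a physician-level random T2 effect beside the family intercept: RANDOM INTERCEPT T2 / SUBJECT=physician. Fit by REML with Kenward-Roger degrees of freedom. If the new component is estimated at zero, keep physician-level df (number of physicians minus 2); this needs a stated override. Write the random effects and the df rule into the SAP, including whether the two physician effects may covary. Use the same structure for the SAP's other longitudinal outcomes. Only the K − 2 rule was simulated, not Kenward-Roger itself. It can be conservative when change hardly clusters: one run at ICC 0.01 gave 3.1%.

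The cost is one variance component, a df rule and some precision. At 40 × 4 the 95% interval widens by (1.73 × 2.02)/(1.67 × 1.98) = 1.06, about 6%, if change does not cluster. At ICC 0.1 it widens by (1.98 × 2.02)/(1.68 × 1.98) = 1.20, about 20%. No new data are needed; if the model has already been run, it can be refitted.

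For length of stay, use a clustered rank-sum test or a permutation test on physician labels.
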